#### Part A: Household sociodemographic characteristics

Person	Age	Sex 1=F 2=M 3=O	Education Primary school=1 High school= 2 University= 3 No= 4	During this year, did you or anyone in your household have DZC? 1=Dengue 2=Zika 3=Chikunguna 4=No	Which month?	Did you go to the doctor or health unit? 1=Yes 2=No	During the day, where do you spend most of the time (7 am -5 pm)? 1=Inside neighborhood, 2=Outside neighborhood
1							
2							
3							
4							
5							
6							
7							
8							
9							
10							
11							
12							

#### Part B: Practices on dengue and water use

Mark the correct answer

**2. Do you apply some type of vector control in your laundry tank to prevent dengue?**

1= Use of fish 2 = Addition of chlorine 3= Use of tank lid 4=Washing and brushing 5= None 6=I don't know

**3. Has the health service applied any type of powder or tablet insecticide in your laundry tank this year?**

1= Yes 2= No 3= I don't know

**4. Which deposits do you use for water consumption?**

1= Ground tank 2=Tap water 3=Other deposits, specify \_\_\_\_\_ 4=None

**5. Do you know where mosquitoes lay their eggs or where they breed?**

1=Clean water 2=Dirty water (e.g. puddle) 3= Grass or pasture 4= I don't know

**6. ¿ which of these media would you like to receive information about dengue? (Multiple choices)**

1=TV 2=Radio 3=Cell phone 4=Internet 5=Newspaper 6=Flyer 6=Visit to your home by a technician 7=Loudspeakers 8=I don't know

#### Part C: Willingness of the community to receive the insecticide coating

**7. Would you like to apply freely a transparent coating as a control method in your laundry tank?**

1 = Yes 2=No 3= I don't know

Thanks for your participation

(Spanish version)

Estamos evaluando una nueva estrategia contra el dengue. Si me permite le realizaré unas preguntas cortas que no le quitarán mucho tiempo. Si usted se siente incómodo con alguna pregunta, puede no contestar o terminar la entrevista cuando lo deseé.

Código casa: \_\_\_\_\_

Código conglomerado: \_\_\_\_\_

**8. ¿Podría darnos los siguientes detalles sobre las personas que viven en la casa, incluyéndose en la siguiente tabla?**

**SECCIÓN A: Características Sociodemográficas del hogar**

Persona	Edad	Sexo 1=F 2=M 3=O	Educación Primaria=1 Bachillerato= 2 Universidad= 3 No= 4	¿En este año ud. o alguien de su hogar tuvo DZC? 1=Dengue 2=Zika 3=Chikunguna 4=No	¿En qué Mes?	¿Asistió al médico o unidad de salud? 1=SI 2=No	¿Durante el día, donde permanece la mayor parte del tiempo (7 am - 5 pm)? 1=En mi hogar o barrio, 2=Fuera del barrio
1							
2							
3							
4							
5							
6							
7							
8							
9							
10							
11							
12							

**SECCIÓN B: Prácticas sobre el dengue y uso del agua**

Marque la respuesta correcta

**9. ¿Usted aplica algún tipo de control en su tanque de lavadero para prevenirse del dengue?**

1= Uso peces 2 = Adición de cloro 3= Uso tapa tanque 4=Lavado y cepillado 5= Ninguno 6=No sé

**10. ¿En este año el servicio de salud ha aplicado algún insecticida tipo polvo o pastilla en su tanque de lavadero?**  
1= Si 2= No 3= No sé

**11. ¿Cuáles de los depósitos usa para el consumo de agua?**  
1= Tanque bajo 2=Agua de la llave 3=Otros depósitos, especifique 4=Ninguno

**12. ¿Sabe usted en dónde ponen los mosquitos sus huevos o dónde se crían?**  
1=Aqua limpia 2=Aqua sucia (charco) 3= Monte o Pasto 4= No sé

**13. ¿Con cuál de estos medios le gustaría recibir información sobre el dengue? (opción multiple)**  
1=TV 2=Radio 3=Celular 4=Internet 5=periódico 6=Volante 6=Visita a su casa por técnico 7=Perifoneo 8=No sé

**SECCIÓN C: Disposición de la comunidad para recibir el recubrimiento insecticida**

**14. ¿Le gustaría que pongamos una pintura transparente como método de control de forma gratuita en su tanque de lavadero?**

1 = Si 2=No 3=No sé

Gracias por participar

## Entomological survey

## Form for extraction of entomological data

**House code:** \_\_\_\_\_ **Cluster:** \_\_\_\_\_

**Inspector:** \_\_\_\_\_

Date: \_\_\_\_\_

**Building type:** House:  Car store:  Health unit:  Church:  Grocery store:  School:  Restaurant:  other:  Public space:

Comment:

(Spanish version)

Código casa: \_\_\_\_\_

Conglomerado: \_\_\_\_\_

Inspector: \_\_\_\_\_

Fecha: \_\_\_\_/\_\_\_\_/\_\_\_\_

Tipo de edificación: Casa: \_ Taller: \_ Unidad de salud: \_ iglesia: \_ Tienda: \_ Colegio: \_ Restaurante: \_ otro: \_ Espacio Público: \_

No.	*Tanques de agua		Otros depósitos con agua		*Detalles de cada tanque de agua	Índices entomológicos	Medidas
	Cemento	Plástico	Tanque bajo	Tanque almacenamiento			
1							
2							
3							
4							
5							
6							
7							
8							
9							
10							
11							
12							
13							
15							
16							
17							
18							

Observación: \_\_\_\_\_

Control of Aedes breeding sites with a dual-action insecticidal coating is effective in reducing Dengue transmission: Cluster-randomised Controlled Trial Study

Statistical Analysis Plan

Ubication of study: Metropolitan Area of Cucuta, Colombia

Approval of the protocol: 11 March 2019

Statistical Analysis Plan

Study design and sample size

This is design study for a large cluster randomized trial on the impact of treating water containers with a protective paint. The sample size was calculated for detection of a 50% reduction in the House Index with > 99% power at 5% significance level. Given a baseline HI of 30%, an intra-cluster correlation coefficient (ICC) of 0.01 and a cluster size of 2,000 households it was found that a minimum of 12 clusters per study arm was needed [1]. The same result but with a lower power (68%) was found for a baseline DZC incidence of 3% and a 50% reduction in the intervention arm. A large number of households per cluster was needed as *Ae. aegypti* vectors are day-biters [2] and it was assumed that many household members stay within their neighbourhoods during the day (mainly housewives, small children and school children when the school is close to their house) where they are at risk to get infected. All estimations were done through The Shiny CRT Calculator which is a web-based app to determine sample size and power for cluster trials [3,4].

Data management and analysis

Descriptive analyse and double data entry was practiced (to minimize data entry errors) into a database using Microsoft Office Excel software by an assistant and supervised by the research team. The analysis was done using SPSS software version 28.0.1.1.

Socio-demographic data were entered in a database. We assessed the frequency of variables potentially associated with the outcomes of recent dengue virus infection (sex, age, educational level, peoples` mobility) and selfreported dengue fever in household members (5). Persons' Chi-square test (χ^2) was applied to determine the differences between population characteristics and DZC selfreported cases, and peoples` mobility across all settings. All statistical analyses were performed at a 0.05 significance level.

Entomological indices were analysed per cluster and overall to show the presence, distribution and abundance of *Ae. aegypti* and the breeding sites most productive for adult mosquitoes were identified [6].

House index (HI): Percentage of houses infested with larvae and/or pupae.

Container index (CI): Percentage of water-holding containers infested with larvae or pupae.

Breteau index (BI): Number of positive containers per 100 houses inspected.

Pupae per person (PPI): Number of pupae per person in each household. To estimate the pupal count for large container (more than 20 L) the methodology by Romero-Vivas [7] was used: According to water level, the number of pupae found was multiplied by a calibration factor.

For the before-after comparison and intervention vs. control arm the difference-in-differences (DiD) approach was applied, taking into account the clustering effect, and estimating the statistical significance through the P-value. Likewise, the reduction of dengue cases reported by SIVIGILA was estimated, according to the annual dengue incidence in intervention and control clusters [8]

Ethical considerations

The household questionnaire was only applied to adults who provided information related to the purpose of this study. No child or adolescent below the age of 18 was interviewed in this study. All people participating in the study were informed in local language through the study information sheet in a written and oral way. They were asked to sign the informed consent form. All participants were informed that their participation was voluntary and that their responses remained anonymous, therefore the study used numbers which replaced the names of individuals and codes which replaced the address of house. Before examining the domestic and peri-domestic water-holding containers, the field team requested permission to enter the house, did the inspection and collected entomological and sociodemographic data.

The study received approval from local health authorities in Cucuta and Norte de Santander and the study protocol was approved by the ethical committee of the Albert-Ludwigs-Universität (application number 141/19) in Freiburg, Germany

References

Article PubMed PubMed Central Google Scholar

1. DANE. Censo Nacional de Población y vivienda 2018. <https://geoportal.dane.gov.co/geovisores/sociedad/cnpy-2018/>. Accessed 30 Apr 2021.

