## Sampling procedure for household survey and entomological inspections

On the basis of available maps, the city was stratified into high, middle and low endemic/infested areas for *Ae. aegypti* (strata) using the surveillance information from SIVIGILA of the preceding year as well as information obtained from interviews with the vector control coordinators in Cúcuta. By this way, 24 high and medium endemic areas (clusters) were selected in Cucuta (16 clusters), Los patios (4 clusters) and Villa del Rosario (4 clusters). Figure 1 shows the selected clusters in

Cucuta to be sampled by staff. For the baseline study they were not yet paired and allocated to the intervention and control arm as this was planned to do with the information resulting from the baseline study enabling us to find pairs of clusters with similar characteristics. The following characteristic should be similar in each pair of clusters: (I) High and middle level endemicity for *Aedes*-borne diseases; (II) Similar socio-economic conditions; (III) Similar types of the built environment: houses, schools, industry, health centers, workshops, churches and stores; (IV) Similar characteristics of public spaces. Within each cluster, all blocks of houses were inspected including public spaces. For the entomological/socio-demographic household survey, a proportion of 10% of 2000 houses was sampled in this study, resulting in 200 houses in each cluster. This number was rounded to 250 by convenience. Therefore, the study targeted 6000 households (250 households in each cluster) using a systematic random sampling method. For this we first estimated the sampling interval by dividing the total number of households in each cluster (around 2000) by the number of sample households (250), resulting in a sampling interval of 8. All households located within each cluster were mapped and a randomly defined starting point was selected and from there every 8th household was visited. Clear replacement rules were given to the interviewers and the compliance was checked in sample of families.

Vector control staff and trained interviewers participated in the survey. They were divided into “couples” of one vector inspector and one interviewer. Each couple was assigned one cluster where they had to visit the sample houses. The interviewer did the interview with the head of household and simultaneously the inspector (local vector control staff) did the inspection of water containers both of them filling a form.

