## Dengue surveillance and case definition

Data of the national surveillance system were obtained from SIVIGILA (the national health surveillance system), aggregated by year and setting (study areas) over the study period. Notified dengue cases including those classified as dengue fever (DF) and severe dengue, relying on a clinical case definition or lab confirmed or hospitalized patients. This study used annual population data (from the National Institute of Statistics-DANE; [10]) for calculating the incidence rate.

[figure not shown]

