## Household questionnaire

### Form for extraction of socio-demographic data

*We are evaluating a new strategy against dengue. If you allow me, I will ask a few short questions that will not take up much of your time. If you feel uncomfortable with any question, you cannot answer or end the interview whenever you want.*

House code: \_\_\_\_\_

Cluster code: \_\_\_\_\_

**1. ¿ Could you give us the following details about the people who live in your house, including yourself in the following table?**

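### The survey chi-square tests ignore household and area correlation, so their p-values can miss the nominal 5% level in either direction; the treatment comparison is unaffected

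*SAP*

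**What the plan says.** The SAP (Data management and analysis) states that Pearson's chi-square "was applied to determine the differences between population characteristics and DZC selfreported cases, and peoples` mobility across all settings" and sets a 0.05 level for all analyses. It names no household, area or survey-design adjustment for these tests. The only such statement concerns the before-after and between-arm comparison, where "the difference-in-differences (DiD) approach was applied, taking into account the clustering effect".

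The data behind the tests are persons within households within areas. The respondent is asked "Could you give us the following details about the people who live in your house, including yourself in the following table", and the form has one row per member, with columns for self-reported dengue, Zika or chikungunya (DZC) and for daytime location (Protocol, Household questionnaire, Part A). On sampling, "the study targeted 6000 households (250 households in each cluster) using a systematic random sampling method" (Protocol, Sampling procedure). There are 24 areas: 16 in Cucuta, 4 in Los Patios and 4 in Villa del Rosario. They were identified from strata drawn up "using the surveillance information from SIVIGILA of the preceding year as well as information obtained from interviews with the vector control coordinators in Cúcuta".

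The SAP does not say what it means by settings. The nearest gloss is in the Protocol (Dengue surveillance and case definition), for notified cases: "aggregated by year and setting (study areas) over the study period".

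**The concern.** Pearson's chi-square assumes independent persons. Members of one household share a home, a water tank and one informant, and households in one area share much of their exposure. The SAP recognises correlation within clusters when it computes sample size (ICC 0.01) and when it specifies the DiD, but not here.

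The size of the error depends on a sentence that can be read in at least three ways: mobility compared across three municipalities, mobility compared across 24 areas, or characteristics crossed with DZC and with mobility, pooled over all areas. It also depends on whether inference stops at these 24 areas or extends to the wider municipalities. At stake is whether reported associations with self-reported disease and mobility can be taken at their stated significance.

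**Working it through.** **Inputs from the documents.** 24 areas (16, 4, 4); 250 households sampled from about 2,000 in each; level 0.05; ICC 0.01 (SAP, Study design and sample size).

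**Assumed inputs.** Household size h of 3 to 5, so m = 250h = 750 to 1,250 persons per area; all household ICCs; all trait ICCs. The area ICC of 0.01 is borrowed from the sample-size section, and 0.001 is tried beside it.

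**1. The plan's own figure.** The documents give no figure for the chi-square tests. The ICC is used only in the power calculation, which reproduces. Design effect (DE) = 1 + 1,999 × 0.01 = 20.99. Effective number per arm = 12 × 2,000 / 20.99 = 1,143.4. Two-sided 5% power for 3% versus 1.5% is 67.7% (stated 68%). For a House Index of 30% versus 15% it is above 99.9% (stated > 99%).

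**2. Formula for the true size.** Size = P(χ² > c/DE), where c is the 5% critical value: 3.84 on 1 df, 5.99 on 2 df, 35.17 on 23 df.

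**3. Comparisons limited to these 24 areas.** Only household correlation enters: DE = 1 + (h − 1) × household ICC.

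| h | Household ICC | DE | Three municipalities (2 df) | 24 areas (23 df) |
|---|---|---|---|---|
| 3 | 0.01 | 1.02 | 5.3% | 5.9% |
| 3 | 0.2 | 1.40 | 11.8% | 34.4% |
| 4 | −0.05 | 0.85 | 2.9% | 1.1% |
| 4 | 0.05 | 1.15 | 7.4% | 13.3% |
| 4 | 0.1 | 1.30 | 10.0% | 25.4% |
| 5 | 0.01 | 1.04 | 5.6% | 6.8% |
| 5 | 0.2 | 1.80 | 18.9% | 67% |

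Over positive ICCs of 0.01 to 0.2 the ranges are about 5% to 19% and 6% to 67%. With a negative household ICC both fall below 5%.

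**4. Finite population.** If the target is the actual residents of these areas, sampling 1 household in 8 brings in a factor of 1 − 1/8 = 0.875. With h = 4 and household ICC 0.05, DE = 1.15 × 0.875 = 1.006, and the 2 df size falls from 7.4% to 5.1%.

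**5. Three municipalities with wider inference, area correlation only.** DE = 1 + (m − 1) × area ICC. At 0.01, m = 750, 1,000 and 1,250 give DE 8.49, 10.99 and 13.49, and sizes of 70%, 76% and 80%. At 0.001, DE is 1.75, 2.00 and 2.25, and the sizes are 18%, 22% and 26%.

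**6. Trait by DZC, pooled over areas (1 df).** DE = 1 + (h − 1) × (product of the two household ICCs) + (m − h) × (product of the two area ICCs). Take h = 4, m = 1,000, household ICC 0.2 for the trait and 0.1 to 0.3 for DZC.

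| Trait area ICC | Size at DZC area ICC 0.01 | Size at DZC area ICC 0.001 |
|---|---|---|
| 0 | 5.7–7.1% | 5.7–7.1% |
| 0.01 | 6.9–8.3% | 5.8–7.2% |
| 0.05 | 11.6–13.0% | 6.3–7.7% |
| 0.1 | 17.2–18.4% | 6.9–8.3% |
| 0.2 | 26.2–27.1% | 8.1–9.5% |

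The largest entry is DE = 1 + 3 × 0.2 × 0.3 + 996 × 0.2 × 0.01 = 3.172, size 27.1%. A trait with no household or area correlation has DE = 1 and stays at 5%. Trait by mobility follows the same formula with mobility's ICCs, which are unknown.

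**7. Simulation check.** With 24 areas, 250 households and 4 persons, sex against DZC rejected about 5% of the time when sex was independent within households, and 3% to 4% when it was balanced within them. Comparisons across municipalities at area ICC 0.01, with household correlation added, rejected about 76% to 78%.

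**The case against.** The strongest reply has four parts.

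- **Direction.** Inflation is not certain. The SAP itself assumes that housewives, small children and school children stay in the neighbourhood. If other members go out, mobility varies within the home, the household ICC may be negative, and p-values would be too large. This stands, and it rules out saying that these p-values are always too small.
- **Largest figures.** The 70% to 80% in step 5 needs the areas to stand for other areas of their municipalities. They were chosen from surveillance data and coordinator interviews, and the only gloss of setting points to study areas. This stands: that reading is the less supported one.
- **Assumed inputs.** Every household and trait ICC is assumed, and 0.01 was set for other outcomes. In step 6 the top row of 26% to 27% gives the trait the same correlation within areas as within households, which is an extreme case. Inference to actual residents shrinks the fixed-area figures further. All of this limits the magnitudes. It does not supply the missing adjustment.
- **Importance.** These are survey association tests. The DiD is stated to take clustering into account, and neither document uses these p-values for pairing clusters or for the trial's conclusion. This stands, and it sets the severity.

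Calling the tables descriptive is not a full answer, because the SAP attaches a test and a 0.05 threshold to them.

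**Conclusion.** The point holds, at minor severity. An independence-based test is prescribed for data with two levels of nesting, so its level is nominal only for variables uncorrelated within households and areas. That the adjustment is missing is clear from the text. The sizes are illustrative and rest on the assumed household size and ICCs.

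A reader might infer three stronger things that the documents do not support:

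- **That all the survey p-values are too small.** The sign of the household correlation is unknown, notably for mobility, and a trait such as sex stays near or slightly below 5%.
- **That comparisons across settings are wrong most of the time.** This holds only for municipalities with wider inference at ICC 0.01. With the areas fixed and a household ICC of 0.01, the municipal comparison is at 5.3% to 5.6%, in practice 5%.
- **That the trial's result is in doubt.** The treatment comparison is a separate analysis.

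The undefined word settings is missing detail, not an error in itself. It matters because it decides which replacement test applies.

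**What to change.** State which variables are crossed, what settings means, and whether inference is limited to these 24 areas. Then replace the plain chi-square with the test that fits:

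- **Trait by DZC or trait by mobility:** Rao-Scott test with cluster as primary sampling unit (24 − 1 = 23 df).
- **Comparisons limited to these 24 areas, by area or by municipality:** Rao-Scott test with household as unit and cluster as stratum, with a finite-population correction if the target is the actual residents.
- **Municipalities with wider inference:** F test on the 24 cluster proportions (2 and 21 df).

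In simulations at nominal 5% with positive or zero correlation and no finite-population correction, these tests rejected about 4% to 6% of the time under their own reading. The household-unit test would still reject 67% (area ICC 0.01) or 15% to 17% (0.001) if wider inference across municipalities were meant, so the target must be fixed first. If no inference is intended, label the tables descriptive and omit the p-values.

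**Cost.** A few added SAP sentences and a rerun; the forms already carry house and cluster codes, so no new data are needed. The cluster-level F test has less power because it rests on 24 values.

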## Study design and sample size to baseline study and evaluation

This is design study for a large cluster randomized trial on the impact of treating water containers with a protective paint. The sample size was calculated for detection of a 50% reduction in the House Index with > 99% power at 5% significance level. Given a baseline HI of 30%, an intra-cluster correlation coefficient (ICC) of 0.01 and a cluster size of 2,000 households it was found that a minimum of 12 clusters per study arm was needed [3]. The same result but with a lower power (68%) was found for a baseline DZC incidence of 3% and a 50% reduction in the intervention arm. A large number of households per cluster was needed as *Ae. aegypti* vectors are day-biters [4,5,6] and it was assumed that many household members stay within their neighbourhoods during the day (mainly housewives, small children and school children when the school is close to their house) where they are at risk to get infected. All estimations were done through The Shiny CRT Calculator which is a web-based app to determine sample size and power for cluster trials [7].

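### Education and mobility are tested against self-reported DZC by crude chi-square in residents of all ages, so a difference in DZC risk by age can appear as an association with either trait

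*SAP*

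**What the plan says.** The SAP, under Data management and analysis, lists the traits to be examined as "sex, age, educational level, peoples` mobility) and selfreported dengue fever in household members". It then states that a Pearson chi-square "was applied to determine the differences between population characteristics and DZC selfreported cases", and adds that "All statistical analyses were performed at a 0.05 significance level". No covariate, stratum, age limit or regression is named for this part in either document.

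The people tabulated are everyone on the household roster. The questionnaire asks for "details about the people who live in your house, including yourself", with no lower age limit. The ethics text says that "No child or adolescent below the age of 18 was interviewed in this study", so children's data are in the table but come from an adult informant.

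Part A of the questionnaire codes schooling as "Education Primary school=1 High school= 2 University= 3 No= 4" and daytime location as "1=Inside neighborhood, 2=Outside neighborhood". The protocol's sample-size section describes those who stay in the neighbourhood by day as "mainly housewives, small children and school children when the school is close to their house".

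**The concern.** Education is partly age by construction. On this form a two-year-old fits no code but *No*, and a pupil of eight fits *Primary*. The *No* row then mixes unschooled adults with preschool children, while the *University* row holds almost only adults. Mobility is tied to age, and through housewives to sex, by the protocol's own description. Age is also on the SAP's list of traits possibly related to infection.

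A trait that moves with age, tested one at a time against an outcome that may move with age, is confounded by age. Correcting the chi-square for clustering would not remove this, because it concerns what is being compared and not its standard error. At stake is how the risk-group tables are read: a small P-value for education or mobility could reflect only the age mix of the rows.

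**Working it through.** **The plan's figures.** The documents give no number for these chi-square tests. Their power figures concern the arm comparison. The 68% for DZC (3% against 1.5%, 12 clusters of 2,000 per arm, ICC 0.01) reproduces: design effect 1 + 1,999 × 0.01 = 20.99; effective size per arm 24,000 / 20.99 = 1,143; two-sided normal power 67.7%.

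**Inputs.** From the documents: 6,000 households, alpha 0.05, the education and mobility codes, and a design DZC incidence of 3%, used here only as a guide to prevalence. Everything else is assumed:

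- 3.5 persons per household, so 6,000 × 3.5 = 21,000 persons.
- Set A: ages 0–5 10%, 6–11 11%, 12–17 11%, adults 68%. Ages 0–5 coded *No*, 6–11 *Primary*, 12–17 *High school*. Adults 8% none, 30% primary, 42% high school, 20% university. Inside the neighbourhood: minors 85%, adults 50%.
- Set B: under 5 8%, 5–17 20%, adults 72%. Primary/high/university/none: 5/0/0/95%, 60/35/0/5% and 30/45/20/5%. Inside: 95%, 80% and 50%.
- DZC depends on age only, so neither trait has any association at a given age.

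**Formula.** With row shares w, row risks p and overall risk P, the expected chi-square is λ = N Σ w(p − P)² / [P(1 − P)]. The rejection rate is the upper tail of a noncentral chi-square (3 df for education, 1 df for mobility) beyond the 5% point.

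**Set A, DZC 6% in minors and 2% in adults.** P = 0.32 × 6% + 0.68 × 2% = 3.28%.

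- *No* row: share 10% + 0.68 × 8% = 15.44%, of which 10 / 15.44 = 65% are under 6. Risk (10 × 6% + 5.44 × 2%) / 15.44 = 4.6%, against 2.0% for university (OR 2.4). Over all four rows λ = 33.4, p about 3 × 10⁻⁷. That p belongs to the overall 3-df test, not to the *No* against university contrast.
- Mobility: inside (0.272 × 6% + 0.34 × 2%) / 0.612 = 3.8%; outside (0.048 × 6% + 0.34 × 2%) / 0.388 = 2.5%. RR 1.5, λ = 25.9, p about 4 × 10⁻⁷.

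**Set A, 4.5% against 2.5% (ratio 1.8).** Education λ = 8.7, mobility 6.7; rejection 70% and 74%.

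**Set A, ratio 1.25 at the same overall 3.28%.** Adults 3.28% / 1.08 = 3.04%, minors 3.80%. Education λ = 1.20, mobility 0.93; rejection 13% and 16%.

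**Rejection rates with no true association of either trait** (21,000 persons; set B at 3% overall DZC; dash = not tabulated):

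| Child:adult risk ratio | A education | A mobility | B education | B mobility |
|---|---|---|---|---|
| 1.0 | 5% | 5% | 5% | 5% |
| 1.25 | 13% | 16% | 15% | 13% |
| 1.5 | – | – | 44% | 35% |
| 1.8 | 70% | 74% | – | – |
| 2 | – | – | 93% | 80% |
| 3 | >99% | >99% | >99% | >99% |
| 0.5 | – | – | 70% | 55% |

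**Sensitivity (set B).** At ratio 2, with 15,000–24,000 persons and DZC of 1–5%, education is rejected in 33% to 99.9% and mobility in 27% to 97%. With a weaker link between age and mobility (80/70/55% inside, 21,000 persons, DZC 3%), mobility is rejected in 31% at ratio 2 and 67% at ratio 3.

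**Does age adjustment cure it?** In 1,000 simulated data sets per scenario (set B, ratios 1 to 3), an age-stratified Cochran-Mantel-Haenszel test rejected in 4–6% for both traits. Its strata were the bands that generated the data, so confounding within a wide band was not tested.

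**Does a cluster correction cure it?** With an assumed design effect of 2 applied to set A, rejection is still 94–95% at ratio 3 and 39–45% at 1.8. The other figures treat persons as independent.

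**The case against.** The strongest reply is that this is description. The SAP speaks of differences and of variables potentially associated with infection; it nowhere says that education or mobility will be reported as a cause or used for targeting. A crude association is a valid description, and age is on the same list, so an age gradient would be visible beside the other tables. That stands, and it limits the point to the P-values and what is inferred from them.

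Three further objections also stand:

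- A reader might infer that age alone will make these tests significant. The documents do not support that. It also requires DZC risk to differ by age, and no risk by age is given. With no gradient the tests keep their 5% level.
- A reader might infer that a misleading mobility result would undermine the cluster-size argument. That argument rests on day-biting vectors and on how many people stay near home, which a simple frequency can check. It does not rest on an association between mobility and DZC.
- The form gives no instruction for children below school age. Coding them *No* is an inference, and some interviewers may have left the cell blank.

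The link between mobility and age may also be looser than set A assumes: housewives are adults, and school children count only when the school is near. The weaker scenario above shows how much that matters. None of this supplies the missing age adjustment.

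**Conclusion.** The point holds in a conditional form. The SAP's only named test for education and mobility is crude, is applied to all ages, and concerns two traits that the form or the protocol ties to age. If DZC risk differs by age in either direction, significance can arise without any association at a given age: about 13–16% of the time at a risk ratio of 1.25, about 70–75% at 1.8 and nearly always at 3, against 5% with no gradient. These rates rest on assumed household size, age shares, schooling and mobility by age, and independent persons; they illustrate the mechanism and do not predict this survey's results.

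A reader might take this as a flaw in the trial's main result. It is not: the arms are compared by a separate difference-in-differences analysis that accounts for clustering, and the surveillance incidence comparison is also separate. The matter is secondary, but worth correcting because a better analysis needs no new data.

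**What to change.** In the SAP, Data management and analysis:

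1. Keep the crude tables of DZC by education and by mobility as description, without P-values.
2. For mobility, fit a logistic model of each person's DZC on mobility, age band and sex in all residents, with bands narrow enough to separate preschool children, pupils and adults.
3. For education, fit a separate logistic model in adults (18 and over), adjusted for age band and sex.
4. In both models allow for household and cluster correlation, and report odds ratios with confidence intervals.

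Two models are better than one. If minors' education were coded as not applicable in a single all-age model, that code would equal the sum of the under-18 age bands and the model would be collinear.

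Cost: a change of SAP wording and two regressions on variables already on the roster. The education estimate then uses adults only and has a somewhat wider interval.
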